Study objective(s)	
Primary
 
Assessment of the relationship between joint-specific tilmanocept uptake value (TUV_{joint}) and synovial anatomic pathology.IHC assessment of macrophage expression of the CD206 receptor. 
Secondary
 
Assessments of CD68 and CD163 receptor expression levels through IHC microscopy.Classification of synovial anatomic pathology as
Lympho-myeloidDiffuse myeloidPauci-immune fibroid 
Exploratory
 
Determine the relationship between TUV_{joint} and mRNA expression profiles of CD68, CD163, and CD206 as determined by RNA sequencing (RNA-seq).Determine the relationship between TUV_{joint} and the number, size, and intensity of CD68, CD163, and CD206 as determined by (optional) flow cytometry.Evaluate synovial expression of CD3, CD20, CD55, and TE-7 and CD206 in synovial tissue biopsy specimens.Assessment of the relationship between global tilmanocept uptake value (TUV_{global}) and synovial anatomic pathology. 
Safety
 
Evaluate safety through the examination of adverse event (AE) incidence, physical examination findings, and changes over time in laboratory tests, electrocardiograms (ECGs), and vital signs.

Study duration	Up to 45 days
Study drug	Tc 99m tilmanocept
Dose(s) and Route of administration	
Dose: Tilmanocept will be administered at a dose of 150-mcg radiolabeled with 10 mCi (370 MBq) Tc 99m.
 
Route of Administration: Tc 99m tilmanocept will be administered through an intravenous (IV) route of administration in 3 mL using a single syringe, with the dose injected as a slow push into the IV catheter. The preferred site of IV placement will be the left or right antecubital vein. At the completion of Tc 99m tilmanocept administration, a 10-mL sterile normal saline flush will be administered.

Inclusion criteria	
1. The subject has provided written informed consent with HIPAA (Health Information Portability and Accountability Act) or equivalent authorization before the initiation of any study-related procedures.2. Women and men of reproductive potential must use adequate birth control measures (e.g., abstinence, oral contraceptives, intrauterine device, barrier method with spermicide, or surgical sterilization) for the duration of the study.3. The subject is at least 18 years of age and was \geq 18 years of age at the time of RA diagnosis.4. The subject has RA as determined by the 2010 American College of Rheumatology/European League Against Rheumatism (ACR/EULAR) Classification Criteria (score of \geq 6/10 at or before screening).5. The subject has a 28-joint disease activity score (DAS28) of \geq 3.2 (includes the C-reactive protein [CRP] test and visual analog scale [VAS]).6. Subjects receiving traditional DMARDs must have been on therapy for \geq 90 days and at a stable dose for \geq 30 days prior to the first imaging visit (Day 0).7. If the subject is receiving biologic disease-modifying antirheumatic drug (bDMARD) or janus kinase (JAK) inhibitor therapy, they have been at a stable dose $>$ 60 days prior to the imaging visit (Day 0). bDMARD therapy should not be administered less than 4 days prior to the imaging visit.8. If the subject is receiving NSAIDs (nonsteroidal anti-inflammatory drug) or oral corticosteroids, the dose has been at a stable dose for \geq 28 days prior to imaging. The

	
corticosteroid dose should be \leq 10 mg/day of prednisone or an equivalent steroid dose.
 
9. The subject has a hand or wrist joint with a minimum ultrasound gray-scale synovitis score of 2 (range 0 to 3).

Exclusion criteria	
1. The subject is pregnant or lactating.2. The subject size or weight is not compatible with imaging per the investigator.3. The subject is currently receiving radiation therapy or chemotherapy or has received radiation or chemotherapy within the past 5 years.4. The subject has an active malignancy or a history of malignancy within the past 5 years.5. The subject has had a finger, hand, and/or wrist amputation or hand or wrist joint arthroplasty.6. The subject has renal insufficiency as demonstrated by a glomerular filtration rate of < 60 mL/min.7. The subject has hepatic insufficiency as demonstrated by ALT (alanine aminotransferase [SGPT]) or AST (aspartate aminotransferase [SGOT]) greater than 3 times the upper limit of normal.8. The subject has any severe, acute, or chronic medical conditions and/or psychiatric conditions and/or laboratory abnormalities that would impart, in the judgment of the investigator, excess risk associated with study participation or study drug administration that would deem the subject inappropriate for study participation.9. The subject has a known allergy to or has had an adverse reaction to dextran exposure.10. The subject has received an investigational product within 30 days prior to the Tc 99m tilmanocept administration (Day 0).11. The subject has received injectable (e.g., intra-articular, intramuscular, etc.) corticosteroids \leq 8 weeks prior to imaging (Day 0).12. The subject has received any radiopharmaceutical within 7 days or 10 half-lives prior to the administration of Tc 99m tilmanocept (Day 0).13. The subject has an intolerance to anesthetic and antiseptic agents indicated for the synovial biopsy procedure.

	
14. The subject is currently receiving anticoagulants (oral anti-platelet agents are permitted) or has a condition that is contraindicated with ultrasound-guided synovial biopsy e.g., needle phobia.15. The subject has heart failure [New York Heart Association (NYHA) Class III-IV], a demyelinating disorder, or a chronic/latent infection [e.g., +Purified Protein Derivative (PPD) test, Human Immunodeficiency Virus (HIV), Hepatitis B].
Study design	
This is a phase 2b, open-label, multi-center, multinational, non-randomized, single-dose study designed to assess the relationship between quantitative Tc 99m tilmanocept planar imaging and synovial histopathology in subjects clinically diagnosed with RA.
 
Subjects will undergo an imaging assessment of the bilateral hands and wrists followed by an ultrasound-guided synovial biopsy of a select joint at a subsequent visit. Tissue samples from the synovial biopsy procedure will be used for 2 mandatory anatomic pathology evaluations, [1] IHC and [2] RNA-seq, and optional flow cytometry, to provide quantitative and semi-quantitative information regarding joint-specific disease activity. Results from each anatomic pathology evaluation will be correlated with TUV_{joint} on planar imaging to mechanistically assess the relationship between synovial anatomic pathology and TUV_{joint}.
 
The quantitative characterization of Tc 99m tilmanocept uptake will be defined using the standardized computation of TUV_{joint} and TUV_{global} by a central imaging laboratory. TUV_{joint} and TUV_{global} metrics are further described in the NAV3-32 Imaging Manual and NAV3-32 Statistical Analysis Plan. Results from Phase 1 and 2 studies have revealed that TUV_{joint} is a sensitive and specific identifier of Tc 99m tilmanocept localization in joint regions with presumed inflammatory macrophage activity.
 
Anatomic pathology evaluations, including IHC and RNA-seq, will be performed by a central pathology laboratory in accordance with standardized operating procedures (SOPs). Synovial immunofluorescence evaluations will be used to determine the degree of expression of various immune markers including CD3, CD20, CD55, TE-7, CD68, CD163, and CD206. These markers will be evaluated in tandem to observe trends in co-expression and will also be compared with corresponding TUV_{joint}(s). IHC evaluations will also be used to characterize the pathotype of the corresponding synovial specimens (as diffuse myeloid, lympho-myeloid, or pauci-

Option	Description
1	The subject has only 1 metacarpophalangeal (MCP) joint or wrist joint with an ultrasound gray-scale synovitis score of ≥ 2 . This joint will be selected for biopsy.
2	The subject has 2 or more MCP and/or wrist joints with an ultrasound gray-scale synovitis score of ≥ 2 . The joint for biopsy will be selected based on evaluation of corresponding TUV_{joint} . In the first subject with multiple qualifying joints, the joint with the highest TUV_{joint} will be selected; in the second subject with multiple qualifying joints, the joint with the lowest TUV_{joint} will be selected. Selection will proceed in this fashion, alternating between highest and lowest TUV_{joint} .

Visit #1 (Screening; Day -30 to Day -1)

- Informed consent
- Review of study eligibility
- Collection of medical history (including medications)
- Vital sign assessment
- Physical examination (including height and weight)
- Clinical labs

	
• RA-specific labs• Urinalysis• Urine pregnancy for subjects of childbearing potential• 2010 ACR/EULAR score• DAS28 evaluation• Ultrasound synovitis assessment• AE assessment 
Visit #2 (Day 0; Tc 99m Tilmanocept Administration and Imaging)
 
Pre-Tc 99m Tilmanocept Administration
 
• Urine pregnancy test for women of child-bearing potential• ECG up to 30 minutes prior to drug administration• Post-ECG vital sign assessment• AE assessment• Review of concomitant medications 
Tc 99m Tilmanocept Administration: Subjects will receive a single IV dose of 150 mcg tilmanocept radiolabeled with 10 mCi (370 MBq) of Tc 99m.
 
0-30 Minutes Post-Tc 99m Tilmanocept Administration
 
• ECG• Post-ECG vital sign assessment• AE assessment 
60 to 75 Minutes Post-Tc 99m Tilmanocept Administration
 
• AE assessment 
Image acquisition: Static gamma camera scan of bilateral hands and wrists
 
• Clinical labs (after imaging) 
Visit #3 (24-72 hours Post-Tc 99m Tilmanocept Administration; Follow-up Telephone Safety Assessment)
 
• Review of concomitant medications• AE assessment
--	---

	
Visit #4 (Day 3-7; Synovial Tissue Biopsy)
 
• Ultrasound assessment of synovitis• Synovial tissue biopsy of selected joint in accordance with Table 1• AE assessment• Review of concomitant medications 
Visit #5 (5 ± 2 days Post-Biopsy; Follow-up Telephone Safety Assessment)
 
• Review of concomitant medications• AE assessment	
Planned study dates	Start of study recruitment / February 2021	End of Recruitment/ December 2023 End of Study/ March 2024
Planned number of study centers	Up to 10 centers which include sites in the US, UK, and EU	
Sample size	Approximately 12 to 24 joints (final number based on an interim analysis and adaptive design)	
Justification of sample size	The proposed sample size is sufficient to provide an acceptable standard error (approximately 0.15) on the Fisher Z scale and yield an acceptable confidence interval width on the population correlation.	
Primary endpoint	
• The correlation between joint-specific tilmanocept uptake value (TUV_{joint}) and the number and area fraction of CD206 expression as determined by IHC assessment.	
Secondary endpoints	
• The correlation between TUV_{joint} and the number and area fraction of CD68 and CD163 determined by IHC assessments.• Classification of synovial anatomic pathology into
• Lympho-myeloid• Diffuse myeloid• Pauci-immune fibroidtypes as a function of CD68, CD163, CD206, CD3, CD20, CD55, and TE7 expression determined by IHC assessments using a multinomial logistic regression model with TUV_{joint} as a covariate.• The correlation between the expression of CD68, CD163, and CD206.	

Exploratory endpoints	
• The correlation of the expression of CD3, CD20, CD55, and TE7 with CD206 as measured through IHC.• The correlation of TUV_{joint} with the expression of CD206, CD163, and CD68 as measured through RNA-seq.• The number and size of CD206, CD163, and CD68 expressing macrophages as measured through (optional) flow cytometry and their correlation with TUV_{joint}.• The correlation between TUV_{global} and synovial anatomic pathology as determined by IHC assessments.• Classification of synovial anatomic pathology into Lympho-myeloid, Diffuse myeloid, and Pauci-immune fibroid types using a multinomial logistic regression model with TUV_{global} as a covariate.
Safety Evaluations	Adverse events, clinical laboratory results (hematology, serum chemistry, vital signs, ECG)
Plan for statistical analysis	
The following populations will be defined for the study:
 
• Intent-to-Assay (ITA) population – the ITA population includes all subjects who have been enrolled in the study, injected with Tc 99m tilmanocept, received all imaging procedures, and have been biopsied.• Per Protocol (PP) population – Consists of all members of the ITA population without major protocol violations. At least 4 evaluable synovial biopsy samples must be available for a subject to be included in the PP population.• Safety population – Consists of all subjects who are enrolled in the study and injected with Tc 99m tilmanocept regardless of imaging or biopsy status. 
All safety analyses will be conducted on the safety population. All efficacy analyses will be conducted on both the ITA population and PP population.
 
Distributions of all baseline and demographic variables will be summarized for the safety population. Quantitative variables will be summarized by the mean, standard deviation, median, and range. Categorical variables will be summarized by counts and percentages.

	
Primary Efficacy Analysis
 
The primary endpoint will be analyzed by computing the Pearson (product-moment) and Spearman (rank) correlation between the TUV_{joint} for the biopsied joint and 2 measures of macrophage prevalence:
 
• The fraction of CD206-expressing macrophages visible in the microscope field under 4x and 10x power magnification, measured as the area fraction (AF) $AF = \frac{\text{Total Stained Area}}{\text{Total Field Area}} \times 100\%.$ 
• The volume of synovial tissue in the biopsied joint derived from the ultrasound synovitis score (Vol). The final CD206-expressing macrophage count is defined as the product of Vol and AF defined above. 
A 95% confidence interval for the population correlation coefficient measuring the association between TUV and CD206 expression (as measured via IHC) will be computed using the Fisher's Z-transformation method ($Z = \tanh^{-1} r$) and its asymptotic Normal approximation. Statistical summaries of the marginal distributions of TUV_{joint} and CD206 macrophage count will be provided (mean, standard deviation, number of cases, median, and range).
 
Secondary Efficacy Analyses
 
The degree of co-expression of CD68, CD163, and/or CD206 macrophage types will be assessed by calculating the Pearson (product-moment) correlations and Spearman rank correlations among these variables. The marginal distributions will be summarized by calculating the mean, standard deviation, number of cases, median, and range for each variable.
 
The ability of TUV_{joint} to discriminate among lympho-myeloid, diffuse myeloid, and pauci-immune fibroid types will be assessed by fitting a multinomial logistic regression model with RA pathotype as the response variable and TUV_{joint} as the explanatory variable. ROC curves will be generated for the multinomial logistic model using the lympho-myeloid type as the base class. No inferential statistics will be generated for this endpoint.

--	---

	
Exploratory Efficacy Analyses
 
The expression of CD68, CD163, and CD206 biomarkers as assessed using specific modules by RNA-seq in synovial tissue specimens will be measured by calculating the Pearson and Spearman correlation matrices for these variables with TUV_{joint}. Descriptive statistics for the variables (mean, number of complete cases, standard deviation) will be provided.
 
The expression of CD68, CD163, and CD206 biomarkers as measured with optional flow cytometry in synovial tissue specimens will be measured by calculating the Pearson and Spearman correlation matrices for these variables with TUV_{joint}. Descriptive statistics for the variables (mean, number of complete cases, standard deviation) will be provided.
 
The Pearson and Spearman correlation matrices for CD3, CD20, CD55, CD68, CD163, CD206, and TE7 biomarker expressions will be computed for each measurement method (IHC, RNA-seq, and optional flow cytometry). The marginal distributions of all variables will be summarized with descriptive statistics (number of complete data points, means, standard deviations, minima, medians, and maxima).
 
The ability of TUV_{global} to discriminate among lympho-myeloid, diffuse myeloid, and pauci-immune fibroid types will be assessed by fitting a multinomial logistic regression model with RA pathotype as the response variable and TUV_{global} as the explanatory variable. ROC curves will be generated for the multinomial logistic model using the lympho-myeloid type as the base class. No inferential statistics will be generated for this endpoint.

--	--

	
Safety Analyses
 
The safety of Tc 99m tilmanocept will be summarized by tabulating the number and percentage of subjects experiencing AEs, treatment emergent AEs (TEAEs), and serious TEAEs. AEs, TEAEs and serious TEAEs will tabulated by system organ class (SOC) and preferred term (PT).
 
Vital signs, clinical laboratory results, and ECG parameters will be summarized with descriptive statistics (mean, standard deviation, n, median, and range) for the observed values and the change from the baseline value.

--	--

TABLE OF CONTENTS

SYNOPSIS.....	2
LIST OF IN-TEXT FIGURES.....	16
LIST OF APPENDICES.....	16
LIST OF ABBREVIATIONS AND DEFINITIONS OF TERMS.....	17
1 INTRODUCTION	21
1.1 Background and Significance	21
1.2 Previous Nonclinical and Clinical Trial Experience in Tc 99m Tilmanocept	26
1.2.1 Clinical Pharmacokinetics (IV).....	26

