In recent years, synovial biopsy-enabled studies have greatly increased our understanding of the pathological processes occurring within the inflamed joints of RA patients (Orr 2017). An important finding of these studies has been that the inflammatory cell compositions of RA inflamed joints can vary between patients (Townsend 2014, van de Sande 2016). The biopsy specimens obtained from different RA patients can have different numbers and densities of macrophages and monocytes, lymphocytes and lymphocyte containing structures, and fibroblast-like synoviocytes (Orr 2017). These differences in cellular composition suggest that RA inflammation can be divided into 3 pathotypes, referred to as diffuse myeloid, lympho-myeloid, and fibroid, respectively (Dennis 2014, Astorri 2015). High densities of macrophages can occur in both the myeloid and lymphoid pathotypes, whereas the fibroid pathotype is largely devoid of both macrophages and lymphoid cells. These pathotypes are not fully discrete, with some overlap occurring. However, they provide a strong basis for temporal or cytological compartmentalization in RA disease natural history.

Current studies utilizing IHC analyses of synovial biopsies are insufficient to determine the distribution of the various pathotypes in RA patients but suggest that the diffuse myeloid and lympho-myeloid pathotypes are about equally frequent in RA patients with the fibroid pathotype being less common. There is growing evidence that patients with different RA pathotypes respond differently to various therapies, holding out the possibility that determining the RA pathotype of an individual patient's RA can direct the choice of the most effective therapy for that patient (i.e., personalized RA therapy) (Dennis 2014). This is an area of ongoing active investigation in RA therapy research (Pitzalis 2013, Donlin 2018, Mandelin 2018). However, already there is significant evidence indicating that patients with a myeloid-

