8 PROCEDURES AND VARIABLES

8.1 Population Characteristics

8.1.1 Demographics and Other Baseline Characteristics

Twelve (12) to 24 evaluable subjects may be enrolled. Subjects will be men and women aged ≥ 18 years with clinically diagnosed RA who are on stable therapy.

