9.4 Sample Size and Justification

The sample size is expected to be approximately 12 to 24 joints. The final sample size will be determined after the completion of an interim analysis including at least 4 subjects in each pathotype (diffuse myeloid, lympho-myeloid and pauci-immune fibroid). The final sample size will be chosen on the basis of the sponsor's business requirements regarding precision for the estimated correlation between CD206 expressing macrophage density and TUV_{joint}. The final sample size will be at least N = 12. If the rarest pathotype has 25% prevalence in the study patient pool, the expected number of subjects at the interim analysis is N = 16. These needs may be further increased because synovial biopsy fails to recover enough tissue for histological analysis in about 15% of cases ([Wechalekar 2014](#)).

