### **1.3 Sample Size**

The sample size is expected to be approximately 12 to 24 joints. The final sample size will be determined after the completion of an interim analysis including at least 4 subjects in each pathotype (diffuse myeloid, lympho-myeloid and pauci-immune fibroid). The final sample size will be chosen based on the sponsor's business requirements regarding precision for the estimated correlation between CD206 expressing macrophage density and  $TUV_{joint}$ . The final sample size will be at least  $N = 12$ . If the rarest pathotype has 25% prevalence in the study patient pool, the expected number of subjects at the interim analysis is  $N = 16$ . These needs may be further increased because synovial biopsy fails to recover enough tissue for histological analysis in about 15% of cases.

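### Twelve to 24 joints give a Fisher Z standard error of 0.33 to 0.22, not the stated 0.15 (which needs about 48 joints), and the expected interim N of 16 counts only the rarest pathotype

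*Protocol*

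**What the plan says.** The protocol synopsis gives the sample size as "Approximately 12 to 24 joints (final number based on an interim analysis and adaptive design") and justifies it as "sufficient to provide an acceptable standard error (approximately 0.15) on the Fisher Z scale", adding that the resulting confidence interval width is acceptable. Protocol 8.1.1 gives the same range in subjects: "Twelve (12) to 24 evaluable subjects may be enrolled". Protocol 8.5.2 specifies one biopsied joint per subject. The primary analysis (synopsis; Protocol 9.5.3.1; SAP 4.2.1) uses a 95% interval from the Fisher Z-transformation and its normal approximation.

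Protocol 9.4 and SAP 1.3 repeat 12 to 24 joints without the 0.15. They fix the final N after "an interim analysis including at least 4 subjects in each pathotype", on the basis of the precision the sponsor requires for the estimated correlation, and set a floor of 12. On the size of the interim, SAP 1.3 says "If the rarest pathotype has 25% prevalence in the study patient pool, the expected number of subjects at the interim analysis is" 16, and Protocol 9.4 agrees: "the expected number of subjects at the interim analysis is N = 16". Both add that more may be needed because "synovial biopsy fails to recover enough tissue for histological analysis in about 15% of cases".

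**The concern.** Two planning figures do not follow from their own inputs.

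The first matters more. The 0.15 is the only numeric precision figure offered for the sample size in either document, and precision of the correlation is the criterion by which the final N is to be chosen. If no N in the planned range can deliver it, a reader will expect a much tighter interval on the primary correlation than the trial can give, and whoever sets the final N has a benchmark the design cannot meet. The SAP's test of a correlation at or below zero uses the same standard error.

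The second is the interim N. Sixteen looks like the waiting time for one pathotype, while the trigger requires all three to be filled. If so, the plan understates how many evaluable subjects must accrue before the final N can be set.

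**Working it through.** **Standard error: inputs.** N = 12 to 24 (synopsis, Protocol 8.1.1 and 9.4, SAP 1.3). One joint per subject, so joints, subjects and data pairs coincide (Protocol 8.5.2). Fisher Z with normal approximation, 95% (Protocol 9.5.3.1, SAP 4.2.1).

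**Attempt to reproduce 0.15.** On the Fisher Z scale, SE = 1/sqrt(N-3), which does not depend on the correlation.

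- N = 12: 1/sqrt(9) = 0.333, which is 2.2 times 0.15.
- N = 16: 1/sqrt(13) = 0.277.
- N = 24: 1/sqrt(21) = 0.218, which is 1.45 times 0.15.

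Variants do not rescue the figure. At N = 24, 1/sqrt(N-1) gives 0.209, 1/sqrt(N) gives 0.204, and the Spearman form sqrt(1.06/(N-3)) gives 0.225.

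**N that gives 0.15.** N = 3 + 1/0.15² = 3 + 44.4 = 47.4, so 48. If 0.15 is a rounded value (0.145 to 0.155), N runs from about 45 to 50.

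**Effect on the interval.** CI = tanh(atanh(r) ± 1.96 × SE). The documents assume no correlation, so r = 0.5 and 0.7 are illustrations. The smallest observed r whose interval excludes zero is tanh(1.96 × SE).

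| | SE | 95% CI at r = 0.5 | 95% CI at r = 0.7 | Smallest r excluding 0 |
|---|---|---|---|---|
| N = 12 | 0.333 | -0.10 to 0.83 | 0.21 to 0.91 | 0.57 |
| N = 24 | 0.218 | 0.12 to 0.75 | 0.41 to 0.86 | 0.40 |
| As stated | 0.15 | 0.25 to 0.69 | 0.52 to 0.82 | 0.29 |

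**Interim N: inputs.** At least four subjects in each of three pathotypes (Protocol 9.4 and 9.5.6, SAP 1.3 and 2.4); rarest type 25%; tissue failure about 15%. The other two prevalences are not given as numbers. Protocol 1.1 says that "the diffuse myeloid and lympho-myeloid pathotypes are about equally frequent in RA patients with the fibroid pathotype being less common", which with the rarest at 25% suggests 37.5% each. Since neither may fall below 25% and they sum to 75%, the full range is 37.5/37.5 to 25/50.

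**Reproducing 16.** The mean number of subjects until the fourth of a type with prevalence 0.25 is 4/0.25 = 16. This matches the stated figure exactly, but for that one type only.

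**All three types.** Let E be the expected further number of subjects, given how many of each type are still needed. Summing over the types not yet filled, E = (1 + Σ pᵢ × E after one more of type i) / Σ pᵢ, starting from four needed of each. Solved exactly:

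| Prevalences (%) | Expected evaluable | Biopsied (÷ 0.85) | P(trigger met by 16 evaluable) | P(still unmet at 24 evaluable) |
|---|---|---|---|---|
| 25 / 37.5 / 37.5 | 18.6 | 21.8 | 0.435 | 0.129 |
| 25 / 30 / 45 | 19.2 | 22.6 | 0.381 | 0.157 |
| 25 / 25 / 50 | 20.6 | 24.2 | 0.295 | 0.225 |

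A simulation of 100,000 trials agrees, with means of 18.55 and 20.60 for the first and last rows.

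**The case against.** Nothing in the documents defends the 0.15 as written; the arguments concern its importance, its origin and the interim figure.

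- **Synopsis only.** The 0.15 is absent from Protocol 9.4 and SAP 1.3, the final N is to be set after the interim, and the reported interval will be computed from the data. That is so, but the other sections put no precision figure in its place, so nothing corrects it.
- **Possibly a mislabelled scale.** On the correlation scale, (1-r²)/sqrt(N-3) is 0.146 at r = 0.75 and N = 12. At N = 24 it is 0.164 for r = 0.5 and 0.140 for r = 0.6. This is conjecture, because no r is assumed anywhere, and the sentence would still be wrong since it names the Fisher Z scale. It is a good reason to ask the sponsor how 0.15 was derived.
- **Sixteen is only a conditional expectation.** Accrual to the interim follows the trigger, no analysis uses the 16, and the text warns that needs may rise. This stands as to weight: alone, the point would be minor. But the warning concerns failed biopsies, not the two omitted pathotypes.
- **The upper end of 19 to 21 fits the background poorly.** Protocol 1.1 supports the equal split, hence about 19; 20.6 requires 25/25/50. This is fair. The range is given because the prevalences are unstated, and it covers every split with the rarest at 25%.
- **Tissue failure is cited at two rates.** Protocol 1.1 mentions 5% to 10%. At 5%, the equal split needs 18.57/0.95 = 19.5 biopsied rather than 21.8. The 15% is used here because the sample-size sections use it.

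**Conclusion.** Both parts hold. The stated standard error is unattainable at every N in the plan: the true value is 0.33 to 0.22, and 0.15 corresponds to about 48 joints. This rests only on the Fisher Z method the plan specifies and on one joint per subject; no assumed correlation is needed. It must be corrected, because it is the sole numeric justification of precision for the primary endpoint.

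The expected interim size is about 19 evaluable subjects if the other two pathotypes are equally common and at most about 21 if they are not, given the plan's 25% for the rarest. At 15% tissue failure that is about 22 to 24 biopsied. The trigger would be met by 16 evaluable subjects in only about 30% to 44% of trials. These figures depend on the assumed split, and this part is the lesser of the two.

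**What to change.** - **Protocol synopsis.** Ask the sponsor how 0.15 was obtained. If 12 to 24 joints is kept, state the Fisher Z standard error as approximately 0.33 (N = 12) to 0.22 (N = 24) and give the matching 95% limits, for example at r = 0.5 and r = 0.7. If 0.15 is the figure to keep, the range must be reconciled with the roughly 48 joints it implies.
- **Protocol 9.4 and SAP 1.3.** Replace 16 with about 19 to 21 evaluable subjects (about 22 to 24 biopsied at 15% tissue failure), and state the assumed prevalence of the other two pathotypes. If the equal split is adopted, the single figures are about 19 and about 22.

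The cost is wording in three places. No extra patients are needed if the 12 to 24 range is kept, but the stated precision becomes less favourable.
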